9.7. Quality control

Data management for this study will be conducted using standard IQVIA processes. The process will take into consideration any data governance imposed on the data source. All patient-level data is de-identified and fully HIPAA-compliant. After study specific data extraction from the databases, anonymized patient-level linked data extract will be securely transferred to IQVIA's secure server compliant with US data protection laws. Only aggregated, anonymous, cohort-level data are provided to the study sponsor.

The IQVIA Advanced Analytics team employs a two-programmer approach to ensure accuracy and reproducibility of coding, including a multi-point quality control checklist for retrospective database studies. All data are stored on secure servers and are auto-archived and password-protected for any future access requirements. Study documents are retained in a minimum of two secure locations and are only removed or deleted upon written request from the sponsor.

9.8. Limitations of the research methods

This study will have limitations inherent to observational studies involving claims and hospital charge data, as well as limitations related to the study design. Results from retrospective studies must be interpreted with caution and can only establish associations and not cause-and-effect relationships.

Claims data do not provide as much clinical detail as medical records as they are primarily collected for the purposes of payment. Therefore, there is a potential for miscoding or misclassification (e.g., identification of newly treated VTE patients). There is also the potential for under-coding if they are not captured for billing purposes.

Because these are open-source databases, there is a loss of visibility to healthcare activity/consumption at pharmacies, offices and hospitals that do not participate/contribute to the databases. Pharmacy stability requirements will be applied to the index prescription pharmacy at the patient level. Nevertheless, LRx has high prescription coverage (e.g., 63% of retail pharmacies in the US). Over-the-counter products will not be captured.

Unlike administrative health plan claims data, it is not possible to define periods of continuous enrollment (CE). Only proxies can be implemented based on patient activity and pharmacy stability to provide greater assurance that patient healthcare activity within these databases is captured during the study period. The data also lack information on mortality.

Only patients with a hospitalization or outpatient visit to a hospital in the CDM database are present in the CDM database, therefore potentially representing a more severe population.

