9.1.1. Inclusion criteria

Patients must meet all of the following inclusion criteria to be eligible for inclusion in the study:

1. Patients with an inpatient hospitalization with admit date and discharge date between 01 January 2018 and 30 November 2022 (selection window) in CDM with a primary diagnosis of VTE

Note: The admit date of the first hospitalization with primary diagnosis of VTE during the selection window will be flagged. Only patients with overnight stays with discharge date after the admit date (to confirm inpatient stay with overnight admission) will be included in the study.

Note: Number of patients who died during hospitalization (identified from discharge disposition measure) will be reported and these patients will be excluded from the study.

2. With evidence of receiving apixaban or warfarin during the hospitalization

Note: The date of the record with first apixaban or warfarin administration during the hospitalization will be flagged as the start of apixaban or warfarin treatment. Patients will be assigned to the apixaban or warfarin cohort based on this treatment received during hospitalization.

3. With linkage to LRx between 01 July 2017 and 31 December 2022 (i.e. study period)
4. With linkage to Dx during the study period
5. With activity in the 6 months prior to the admit date of hospitalization, defined as ≥ 1 claim in Dx and ≥ 1 prescription claim in LRx (pre hospitalization period)
6. With activity in the 1-month after the discharge date of hospitalization, defined as ≥ 1 claim in Dx and ≥ 1 prescription claim in LRx (variable post hospitalization period)
Note: Patients will have a minimum 1-month post discharge period (to capture outpatient treatment)
7. With age ≥ 18 years on apixaban or warfarin administration date during index hospitalization

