9.2. Variables

[figure not shown]
From the final sample, the following measures will be reported (Figure 2):

1. Patients with a claim for the respective treatment (apixaban for apixaban cohort or warfarin for warfarin cohort; using NDC from LRx) as their first post-discharge outpatient treatment (on or within 30 days following discharge i.e. discharge date or ≤ 30 days after discharge date) (n, %). These patients will comprise the analytic cohort for outcomes assessment.

- a. The date of the first post-discharge outpatient prescription claim in LRx (apixaban or warfarin) will be defined as the ‘treatment index date’ for patients in both cohorts respectively.
 - b. Patients will be required to have pharmacy stability during the 6-month period preceding the treatment index date, defined as consistent reporting of data in each month from the pharmacy associated with the treatment index date in LRx to ensure continuous visibility within LRx. The number of patients excluded due to lack of stability will be reported (n, %)
 - c. Patients with recurrent VTE, major bleeding, or CRNM bleeding between the discharge date and the treatment index date will be excluded. The number of patients excluded due to these reasons will be reported (n, %).
 - d. Patients will be followed from the treatment index date until the earliest of last prescription, last patient medical claim, end of pharmacy stability, or end of study period using the Dx/Rx databases.
2. Patients with OAC (warfarin, apixaban, rivaroxaban, dabigatran, or edoxaban) other than the respective inpatient treatment as their first outpatient prescription claim (on discharge date or within 30 days of discharge) (NDC codes from LRx; n, %). These patients will be captured as having switched from inpatient therapy and will not be further evaluated for outcomes.
 3. Patients with no post-discharge outpatient prescription claim for any OAC (on or within 30 days of discharge) (NDC from LRx; n, %)

All study outcomes will be evaluated for the apixaban and warfarin cohorts.

Figure 2. Study Flow

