9.2.2. Outcome measures

The following outcome measures are assessed post-discharge, and will be measured during the variable post-index period starting on the treatment index date for the apixaban and warfarin cohorts.

Treatment patterns

- Persistent days (mean, SD, median, IQR, min, max) will be reported for patients until they discontinue, switch or end of follow-up based on definitions below
- Patients discontinuing outpatient treatment of apixaban or warfarin, respectively (NDC codes from LRx; n, %)

Note: Discontinuation will be defined as the occurrence of a ≥ 30 day gap from the run-out of days' supply of the treatment (post-discharge) index prescription (i.e. apixaban or warfarin) to the date of the next claim for the respective therapy or with no other claims for the respective therapy. The date of the discontinuation will be defined as the last day of the days' supply of the last filled prescription.

- Time (in days) from treatment index date to discontinuation date (mean, SD, median, IQR, min, max)

Note: Kaplan-Meier (KM) curves will be generated to measure median time (and 95 % CI) to discontinuation.

- Patients switching to an OAC other than apixaban or warfarin, respectively (switched) (NDC codes from LRx; n, %)

Note: Patients will be considered to have switched if they filled a prescription for OAC other than apixaban or warfarin, respectively (identified through NDC codes in LRx) or for PAC within 30 days before or after the run out date of index treatment. The date of the switch will be defined as date of the prescription of such a therapy (OAC or PAC).

- Time (in days) from treatment index date to switch date, defined as the date of the first claim for the new OAC or PAC (mean, SD, median, IQR, min, max)

Note: KM curves will be generated to measure median time (and 95 % CI) to switching

Clinical Outcomes

The following clinical outcomes will be assessed during the time patients are persistent with their respective index apixaban or warfarin treatment (treatment index):

- Patients with ≥ 1 hospitalization for recurrent VTE (ICD-10 codes in CDM; n, %)
- Incidence rate (IR) of recurrent VTE (per 100 patient years)
 - The date of the first observed event will be flagged. The numerator for IR will be the number of patients with the event of interest and denominator will be the ‘at risk’ period i.e. the time to first event. The 95% confidence intervals (CI) will also be reported.

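### Death after discharge is handled neither in the end-of-follow-up rule nor in the discontinuation definition, and in-hospital deaths that the hospital data could show are not used.

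*Combined protocol and SAP*

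**What the plan says.** Section 9.8 lists as a limitation, without qualification: "The data also lack information on mortality". Section 9.1.1 says of the index VTE stay: "Number of patients who died during hospitalization (identified from discharge disposition measure) will be reported and these patients will be excluded from the study".

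Section 9.2 starts follow-up at the first outpatient fill of the index drug after discharge and runs it "until the earliest of last prescription, last patient medical claim, end of pharmacy stability, or end of study period using the Dx/Rx databases". Death is not on that list, and CDM is not a source for it.

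Section 9.2.2 gives persistent days that "will be reported for patients until they discontinue, switch or end of follow-up". Discontinuation is a gap of at least 30 days between run-out and the next index-drug claim, "or with no other claims for the respective therapy". Its date comes from the supply: "The date of the discontinuation will be defined as the last day of the days" (the sentence goes on to name the supply of the last fill). There is no exception for death. The same section reads later CDM admissions for recurrent VTE and major bleeding.

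Section 9.6 treats treatment patterns as the primary endpoint. It plans Kaplan-Meier analyses and a Cox model for discontinuing or switching, with treatment cohort as the main effect.

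**The concern.** A patient who dies while taking the index drug makes no more claims for it. The second limb of the discontinuation definition then fits, although the patient never chose to stop. If the analysis is programmed from 9.2.2, deaths enter the discontinuation percentage, the Kaplan-Meier curve and the cohort hazard ratio. If it is programmed from 9.2, most of the same patients are censored. Two programmers could follow the protocol faithfully and get different primary results.

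The sentence in 9.8 suggests that nothing can be done. Section 9.1.1 shows that at least one kind of death, death during a CDM inpatient stay, is visible in the data. Section 9.6 says that the cohorts will not be compared, but its Cox model estimates an apixaban-versus-warfarin hazard ratio, so any difference in mortality between cohorts could reach a reported estimate.

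**Working it through.** The plan states no death rate, event rate or power figure that bears on this, so there is no figure to reproduce. The check sets the rules side by side and then runs an illustration on assumed rates.

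**The rules applied to two constructed patients**

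| | Patient A | Patient B |
|---|---|---|
| Last index-drug fill and supply | day 60, 30 days | run-out on day 90 |
| Last fill of any other drug | none later | day 95 |
| Last medical claim | day 70 | day 97 |
| In-hospital death | day 75 | day 100 |
| Section 9.2.2 alone | discontinued, day 60 + 30 = 90 | discontinued, day 90 |
| Section 9.2 read literally | follow-up ends day min(60, 70) = 60; censored | follow-up ends day min(95, 97) = 95, if last prescription means any drug |
| 30-day gap after run-out complete | day 90 + 30 = 120, after death | day 90 + 30 = 120, after death |

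For patient A the two sections conflict: an event 15 days after death, or censoring 15 days before it. For patient B they agree on discontinuation on day 90, although only 10 of the 30 gap days had passed at death. The plan does not say that 30 observable days are needed. The literal 9.2 rule therefore does not dispose of every case.

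**Possible size if 9.2.2 prevails**

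Assume constant hazards:
- d = ln 2 / (true median persistence in days)
- m = −ln(1 − annual mortality) / 365
- c = share of deaths that occur in CDM hospitals and are censored
- share of apparent discontinuations that are deaths = m(1 − c) / [d + m(1 − c)]

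Example with a median of 180 days, 5% mortality and c = 0: d = 0.003851, m = 0.0001405, share = 0.0001405 / 0.0039915 = 3.5%.

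| Annual mortality (assumed), median 180 days | c = 0 | c = 0.4 |
|---|---|---|
| 2% | 1.4% | 0.9% |
| 5% | 3.5% | 2.1% |
| 10% | 7.0% | 4.3% |

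Over assumed medians of 120 to 365 days and mortality of 2% to 10%, with c = 0, the share runs from 0.9% to 13.2%.

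For the hazard ratio, apparent HR = [HR × d_W + m_A(1 − c)] / [d_W + m_W(1 − c)], where A is apixaban and W is warfarin. Assume a true HR of 0.80 and a warfarin median of 180 days.

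| Annual mortality, apixaban / warfarin (assumed) | Apparent HR, c = 0 | Apparent HR, c = 0.4 |
|---|---|---|
| 5% / 5% | 0.807 | 0.804 |
| 5% / 10% | 0.778 | 0.787 |
| 10% / 5% | 0.844 | 0.827 |

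The distortion can go either way. Censoring the captured deaths reduces it but does not remove it.

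**The case against.** The strongest reply is that the protocol nowhere says that deaths count as discontinuation. A reader might infer it from 9.2.2, but 9.2 closes follow-up at the earliest of its end points, and a patient who dies with supply in hand has a last fill before run-out. Read literally, that patient is censored. This stands for most deaths on treatment. It does not settle precedence, and it does not cover deaths in the gap after run-out.

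A reader might also infer that the deaths already identified are being misclassified. They are not: 9.1.1 concerns the index stay, and those patients are excluded before any treatment index date. That the disposition field can be used for later stays is a reasonable inference, because 9.2.2 reads those stays for outcomes, but it is not stated.

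It is tempting to say that mortality inflates discontinuation more in one named cohort, or to put a figure on the shift. The documents give no death rate and do not say which cohort is sicker, so neither is supported. In the illustration the shifts in the hazard ratio are modest.

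Nor does leaving disposition unread by itself lose recurrent VTE or bleeding events. A qualifying admission counts whether or not it is fatal. An admission after the last fill may fall outside follow-up, but that comes from the last-prescription end point.

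Finally, 9.8 does disclose the gap, and its sentence remains true for deaths outside contributing hospitals.

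**Conclusion.** The point holds as a gap in the definitions and a missed, inexpensive reduction of bias. Two parts need no assumption: death after discharge appears in neither 9.2 nor 9.2.2, and the 9.8 sentence is broader than 9.1.1 allows. Whether deaths in fact become discontinuations depends on a precedence rule that the plan does not give.

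The size and direction of any effect are unknown. The ranges above rest on constant hazards, assumed mortality and persistence, an assumed 40% capture where c = 0.4, and the reading in which 9.2.2 prevails. This is a worthwhile improvement to the primary endpoint definition and does not by itself undermine the study.

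**What to change.** 1. In 9.2.2, flag in-hospital death from the discharge disposition of any CDM admission after the treatment index date, once it is confirmed that the field is available for those stays.
2. Where that death comes before a confirmed discontinuation (the full 30-day gap after run-out) or a switch, censor at the death date in the Kaplan-Meier and Cox analyses and do not count the patient as discontinued. Patient A would be censored on day 75 and patient B on day 100.
3. Add a sensitivity analysis by cumulative incidence, with captured death as a competing event. Censoring is the main analysis. The two answer different questions and should not be offered as interchangeable.
4. State that this rule overrides the no-further-claims limb of 9.2.2, and how it fits with the last-prescription end point in 9.2. Merely adding death to the earliest-of list changes nothing, because the last fill comes first.
5. Report the number of captured deaths per cohort.
6. Limit the 9.8 sentence to deaths outside inpatient stays at participating hospitals.

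The programming cost is about one flag from a field that the plan already uses. Section 9.6 says that major changes to primary endpoint definitions go into an amendment, so one may be needed. The drawback is partial capture: deaths at home or in non-contributing hospitals stay invisible and would still be handled by the existing rules.

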9.9. Other aspects

Not applicable.

10. PROTECTION OF HUMAN SUBJECTS

10.1. Patient information

This study involves data that exist in anonymized structured format and contain no patient personal information.

All parties will comply with all applicable laws, including laws regarding the implementation of organizational and technical measures to ensure protection of patient personal data. Such measures will include omitting patient names or other directly identifiable data in any reports, publications, or other disclosures, except where required by applicable laws.

10.2. Patient consent

As this study involves anonymized structured data, which according to applicable legal requirements do not contain data subject to privacy laws, obtaining informed consent from patients by the Alliance is not required.

10.3. Institutional review board (IRB)/Independent ethics committee (IEC)

Not applicable.

11. MANAGEMENT AND REPORTING OF ADVERSE EVENTS/ADVERSE REACTIONS

This study involves data that exist as structured data by the time of study start.

In these data sources, individual patient data are not retrieved or validated, and it is not possible to link (i.e., identify a potential association between) a particular product and medical event for any individual. Thus, the minimum criteria for reporting an adverse event (AE) (i.e., identifiable patient, identifiable reporter, a suspect product, and event) cannot be met.

12. PLANS FOR DISSEMINATING AND COMMUNICATING STUDY RESULTS

Tables of study results will be shared with the Alliance throughout the analytic phase of the study. The draft and final study report will be provided to the Alliance upon completion of the analytic phase.

In the event of any prohibition or restriction imposed (e.g., clinical hold) by an applicable competent authority in any area of the world, or if IQVIA is aware of any new information which might influence the evaluation of the benefits and risks of an Alliance product, Alliance should be informed immediately.

14. LIST OF TABLES

Not applicable

15. LIST OF FIGURES

Figure 1: Study Period

Figure 2: Study Flow
